### **Handling of missing values/censoring/discontinuations**

Patients without parasite clearance for whatever reason will be censored at the time of last parasite assessment.

Patients who did not have fever at baseline will not be included in the analysis of FCT. Patients without fever clearance for whatever reason will be censored at the time of last temperature assessment.

In case that a patient receives rescue medication before (parasite or fever) clearance, the time to event will be censored at the first use of rescue medication.

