In the current study, KAE609 will be given to patients with uncomplicated symptomatic *P. falciparum* malaria. KAE609 is expected to reduce the number of circulating malaria parasites in the blood of patients and consequently improve their clinical symptoms within the first 24 hours. There is also the possibility of complete cure of their illness.

The risk of developing resistant strains of parasite is possible but low in this small study.

KAE609 has been earlier evaluated in adult patients with acute, uncomplicated malaria due to *P. falciparum* mono-infection at doses of 75 mg in a PoC extension study and 30, 20 mg, 15 mg and 10 mg in a Minimum Inhibitory Concentration (MIC) study (Hien et al 2017). In the MIC study, treatment failure due to recrudescence was reported in 4 (36%) patients and one patient had late treatment failure due to new malaria infection in the PoC extension study at 75 mg dose. There were no patients with early treatment failure (ETF) in the 30 mg and 15 mg dose groups while three patients from the 10 mg dose group (42%) and one patient from the 20 mg dose group (25%) were ETFs.

The risk of any treatment failure (see [Section 6.5.8](#)), recrudescence or new infection in this study will be managed with rescue medication in the form of standard-of-care pharmacotherapy (Coartem). This may minimize the likelihood of resistance emergence or spread of infection.

The current study will include only adult patients (≥ 18 years) suffering from uncomplicated symptomatic *P. falciparum* malaria. Given the expected sub-therapeutic efficacy of the doses of KAE609 in the first 2 cohorts, only a small number (N=10) of patients to assess safety events will be included (10 mg SD, 25 mg SD and 10 mg 3 Days). Following acceptable safety results in these cohorts, higher doses (25 mg 3 days and 50 mg SD or higher) with an increased number of patients (20 patients) will be enrolled in the study. Thereafter, the dose of KAE609 may be increased sequentially up to 225 mg based on continuous monitoring of safety.

This is the first time that KAE609 will be tested in African patients. All previous studies involved Asian and Caucasian participants only.

4 Population

The study population will consist of male and female patients (≥ 18 years old and ≥ 45 kg) with confirmed and uncomplicated symptomatic *P. falciparum* malaria.

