5.5.4 Instructions for prescribing and taking study treatment

KAE609

KAE609 can be administered irrespective of the timing of food intake.

Study medication will be administered by the study center personnel with approximately 180-240 ml of water. Each subject's mouth must be checked to ensure that the medication was swallowed. In the case that the patient vomits within 30 minutes of intake a replacement dose will be given to the patient and the investigator or designee will notify IRT. If the second dose is vomited the patient has to be given Coartem as rescue medication.

Coartem

Patients will be dosed BID for 3 days (at the following time points: 0, 8, 24, 36, 48, and 60 hours) and must receive a standard meal within 30 min prior to dosing, as per label. In the case that the patient vomits within 1 hour of intake a replacement dose will be given to the patient and the investigator or designee will notify IRT. If the second dose is vomited the patient has to be given non-lumefantrine standard of care.

Conventional 80/480 mg tablets or 20/120 mg tablets are to be taken orally with a glass of water. The dispersible tablet is to be dissolved in 10 mL of water in a small cup, and subsequently administered orally under hospital supervision; thereafter the cup will be rinsed with an additional 10 mL of water and the content is to be swallowed again.

Coartem medication should be followed whenever possible by food/drink (broth, sweetened condensed milk, etc.) as appropriate.

All dosages prescribed and dispensed to the subject during the study must be recorded on the Dosage Administration Record (DAR) CRF.

All kits of study treatment assigned by the IRT will be recorded in the IRT.

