5.5.6 Rescue medication

The following circumstances warrant discontinuation of study treatment and the implementation of rescue medication (see [Section 6.5.8](#)):

Early treatment failure (ETF)

ETF is defined within this protocol as:

1. Clinical decline or lack of improvement (per Investigator) at 24 hours after first dose of treatment.
2. Development of any clinical complications (described in the WHO definition of complicated/severe malaria (WHO Guidelines 2010)) in the presence of parasitaemia within 72 hours of the first dose of treatment
3. Parasitaemia $> 75\ 000/\mu\text{L}$ at or after 12 hours post-dose
4. Parasitaemia \geq baseline with or without fever at 36 hours after first dose of treatment
5. Any parasitaemia based on microscopy with fever, 48 hours post-dose
6. Parasitaemia $> 100/\mu\text{L}$ based on microscopy with or without fever, 72 hours post-dose

Late Clinical Failure (LCF)

Development of danger signs or severe malaria on any day between Study Day 5 and Day 29 in the presence of parasitaemia without previously meeting any of the criteria of ETF.

Presence of parasitaemia and axillary temperature $\geq 37.5^\circ\text{C}$ on any day between Study Day 5 and Day 29 without previously meeting any of the criteria of ETF.

Late Parasitological Failure (LPF)

Presence of parasitaemia on any day between Study Day 5 and Day 29 and axillary temperature $< 37.5^\circ\text{C}$ without previously meeting any of the criteria of ETF or LCF.

Commencement of rescue medication with Coartem may occur after start of trial medications and up to Study Day 28 as deemed necessary by the investigator. Any patient on KAE609 who

did not need rescue medication up to Study Day 28, will be given Coartem at end of the study at Study Day 29. Rescue medication according to local guidance will be used for severe malaria.

Patients randomized to Coartem and meeting treatment failure definition will be further treated by rescue medication as per local treatment guidance.

The patients receiving rescue medication will not be replaced and will not discontinue the study (i.e., all the examinations as per the assessment schedule and all CRF pages for this patient will need to be completed).

Safety blood tests (Full Blood Count (FBC) and blood chemistry) will be collected on the initial day of rescue medication dosing. Blood films and blood sampling for parasite count and genotyping must be taken before giving the rescue treatment.

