**Figure 1-1 Study KAE609A2202 diagram**

Given the expected sub-therapeutic efficacy of the doses of KAE609 in the first 2 cohorts, a smaller number (N=10) of patients will be included (10 mg Single Dose (SD), 25 mg SD and 10 mg 3 Days) to detect potential LFT increases. In the subsequent cohorts a higher number (N=20) of patients will be included. All patients will be followed up for 4 weeks with close monitoring in an inpatient setting for at least the first 3 days (Study Day 4) for efficacy and safety followed by outpatient monitoring up to Study Day 29.

Patients will be randomized to KAE609 vs Coartem in a ratio of 1:1 in cohort 1. In cohort 2, SD KAE vs QD KAE609 vs Coartem will be randomized in the ratio of 1:1:1. In Cohorts 3

and 4 the SD KAE609 vs QD KAE609 vs Coartem will be randomized in the ratio of 2:2:1. In Cohorts 5 and 6 the SD KAE609 vs Coartem will be randomized in the ratio 2:1. There are no stratification factors in this study.

Visits to assess safety and efficacy will be scheduled during the follow-up period as described in the assessment schedule table in protocol.

The safety of entire study will be monitored by the Safety Review Committee.

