## 1.2 Study objectives and endpoints

**Table 1-2 Objectives and related endpoints**

Objective(s)	Endpoint(s)

Primary Objective(s)
 
 
To characterize hepatic safety aspects of single- and multiple ascending doses of KAE609 in adult malaria patients
 
	
Endpoint(s) for primary objective(s)
 
 
At least 2 CTCAE grades increase from baseline in ALT or AST during the 4 week study period
 

Secondary Objective(s)
 
 
To evaluate overall safety and tolerability of KAE609.
 
To assess key PK parameters following treatment with KAE609.
 
To assess the efficacy of KAE609 in patients with uncomplicated falciparum malaria.
 
To assess recrudescence after single and multiple doses of KAE609
 
	
Endpoint(s) for secondary objective(s)
 
 
Standard safety/tolerability assessments (AE incidence and severity, vital signs, ECG, laboratory abnormalities)
 
PK parameters such as AUC, Cmax, Tmax, T1/2 etc.
 
PCR-Uncorrected adequate clinical and parasitological response (ACPR) and PCR-Corrected ACPR at Days 15 and 29 (i.e., 14 and 28 days post-dose)
 
Parasite and Fever Clearance Times (PCT and FCT) before rescue medication is given
 
Incidence rate of recrudescence at Day 29
 

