### **2.7.2.3 Parasite clearance time (PCT) and fever clearance time (FCT)**

Descriptive statistics (mean, standard error, median, quartiles) will be presented for each treatment by cohort using the Kaplan-Meier method. Kaplan-Meier curves will be provided.

PCT will be calculated based on uncorrected parasite counts.

PCT, and FCT will be summarized descriptively by the following subgroup

- Sex (male vs female)

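### Censoring parasite and fever clearance time at rescue is informative, so Kaplan-Meier can overstate, and never understates, the proportion who clear before rescue

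*SAP*

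**What the plan says.** The endpoint in SAP Table 1-2 and Protocol Table 2-1 is "Parasite and Fever Clearance Times (PCT and FCT) before rescue medication is given". SAP 2.7.2.3 gives the estimator: "Descriptive statistics (mean, standard error, median, quartiles) will be presented for each treatment by cohort using the Kaplan-Meier method". Under its heading on missing values and censoring, a patient rescued before clearance is handled so that "the time to event will be censored at the first use of rescue medication". Patients who neither clear nor are rescued are covered by a separate rule: "Patients without parasite clearance for whatever reason will be censored at the time of last parasite assessment". Protocol 9.5.1.3 has the same rules, so the two documents agree.

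Protocol 5.5.6 opens its list of early and late treatment failure criteria with "The following circumstances warrant discontinuation of study treatment and the implementation of rescue medication". Five of the six early failure criteria need parasites to be present; the exception is the investigator's clinical judgement at 24 hours. The late failure criteria need parasites too. There are other routes to rescue. After vomiting of KAE609, Protocol 5.5.4 says "If the second dose is vomited the patient has to be given Coartem as rescue medication", and Protocol 5.6.2 allows rescue at the investigator's discretion after other treatment discontinuations.

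On the low-dose arms, SAP 1.1 says "Given the expected sub-therapeutic efficacy of the doses of KAE609 in the first 2 cohorts, a smaller number (N=10) of patients will be included".

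**The concern.** Kaplan-Meier treats a censored patient as someone who would have gone on to clear at the same rate as those still under observation. A patient rescued for persistent parasites is a poor candidate for that assumption: the rescue happened because the drug was not clearing the infection. Rescue also ends any chance of clearing before rescue, so for the endpoint as worded it is a competing event rather than a loss of information.

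The SAP handles a similar patient differently elsewhere. In the Kaplan-Meier analyses of ACPR (SAP 2.7.2.1.1 and 2.7.2.1.2), a patient whose parasites never clear is counted as an event at Day 7.

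At stake is how the clearance curves and their summaries read in arms with appreciable rescue. A curve could approach 100% cleared in an arm where a sizeable fraction had to be rescued.

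**Working it through.** **Inputs from the documents.** KAE609 arms have 10 patients in Cohorts 1 and 2 and 20 thereafter. Protocol 3.6 cites early treatment failure in earlier work of 42% at 10 mg (three patients), 25% at 20 mg (one patient), and none at 15 or 30 mg. A denominator of 7 for the 10 mg group is an inference (3/7 = 42.9%); the protocol does not state it. The early failure criteria are read between 12 and 72 hours.

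**Inputs assumed.** Clearance times and rescue times appear in neither document. A 5% early failure rate for a 20-patient arm is also an assumption.

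**The plan's own figures.** None is given for PCT or FCT. The figures behind the arm sizes (Protocol 9.8.1) do reproduce: the chance of at least 2 events in 10 is 0.851 at a 30% rate and 0.035 at 3%; of at least 3 in 20, 0.965 and 0.021.

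**Direction.** At each time j let n be the number at risk, c the number clearing and r the number rescued.

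- Kaplan-Meier, rescue censored: S = product of (1 − c/n). Estimated proportion cleared = 1 − S = sum of S(before j) × c/n.
- Aalen-Johansen, rescue competing: O = product of (1 − (c + r)/n). Cumulative incidence of clearance = sum of O(before j) × c/n.

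O is never larger than S, so the Kaplan-Meier figure is never below the cumulative incidence. The two separate only when someone clears after a rescue.

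**Worked 10-patient arms**, each with 6 cleared and 4 rescued and no drop-out, so that the cumulative incidence ends at 6/10 = 60%. Rescue is placed just after the assessment named.

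- Clearance at 8, 8, 12, 12, 12, 24 h; all rescues after 24 h. Nobody clears after a rescue. Kaplan-Meier 60%; no bias.
- Clearance at 12, 24, 24, 36, 36, 48 h; rescues after 24, 36, 48, 72 h. Kaplan-Meier = 1 − (9/10)(7/9)(4/6)(2/3) = 1 − 0.311 = 68.9%. Median 36 h by both methods.
- Clearance at 12, 12, 24, 36, 36, 48 h; all rescues after 24 h. Kaplan-Meier = 1 − (8/10)(7/8)(1/3)(0) = 100%. Median 36 h by both methods.
- Clearance at 36, 36, 36, 48, 48, 60 h; all rescues after 24 h. Kaplan-Meier = 1 − (3/6)(1/3)(0) = 100%. Median 36 h by Kaplan-Meier, 48 h by cumulative incidence.

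A 20-patient arm with one rescue after 24 h and clearances at 12 to 48 h gives 100% against 95%.

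**Simulation**, 4,000 arms per setting. Clearance is log-normal (sigma 0.5), read at the next scheduled smear. Failing patients are rescued at 24, 36, 48 or 72 h with equal chance. The table shows mean overstatement of final clearance (Kaplan-Meier minus cumulative incidence), in percentage points.

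| Assumed median clearance | n=10, 42% failure | n=10, 25% | n=20, 5% | n=20, 0% |
|---|---|---|---|---|
| 8 h | 0.3 | 0.3 | 0.2 | 0 |
| 12 h | 2.0 | 2.0 | 1.0 | 0 |
| 18 h | 7.4 | 6.3 | 2.5 | 0 |
| 24 h | 14.8 | 11.4 | 3.6 | 0 |
| 36 h | 27.9 | 19.1 | 4.7 | 0 |

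At 48 h the 42% failure arm is overstated by 0.3 to 7.3 points over the same range.

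**The case against.** The strongest reply is that the bias may be negligible. The protocol describes KAE609 as fast-acting and expects parasite counts to fall within 24 hours, while most early failure criteria are read at 24 hours or later. If those who clear do so before anyone is rescued, Kaplan-Meier is exact. This stands, and it is why the point must be conditional.

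Nor is failure hidden. SAP 2.7.2.2 reports early and late failure proportions and parasitaemia at 12, 24 and 48 hours per arm with exact intervals, and ACPR is reported too. PCT and FCT are secondary and descriptive, with no hypothesis and no comparison with Coartem. The judgement on whether a regimen is safe for further development rests on the hepatic endpoint and narratives. All of this limits the consequence, but a separate failure proportion does not correct the clearance curve beside it.

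Some rescues, such as after a second vomited dose, are not failures, and their censoring may be less informative. Fever may also resolve before a parasite-based rescue, so FCT may be less affected. Both stand.

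The endpoint wording could be read as merely setting aside data after rescue. Even so, Kaplan-Meier would need rescue to be unrelated to the prospect of clearing, and the failure criteria make that implausible.

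A reader might go further and infer that the plan does overstate clearance most in the low-dose arms and so flattens the dose-response. The documents do not establish that. Earlier early failure rates were not monotone in dose (none at 15 mg, 25% at 20 mg), came from very small groups, and no dose-response analysis of clearance is planned.

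**Conclusion.** The concern holds in a conditional form. Censoring at rescue is informative for most rescued patients. The resulting error in the proportion cleared runs one way, upwards, and no planned analysis addresses it.

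Its size cannot be read from the documents. In a 10-patient arm with 4 rescues it lies between 0 and 40 points in the worked arms. On average at 42% early failure it is 0.3 to 27.9 points for assumed median clearance of 8 to 36 h. At 5% failure and 20 patients it is 0.2 to 4.7 points, and it is zero without rescue. These figures rest on the assumed clearance distribution and rescue times.

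A larger effect in the low-dose arms is likely, because sub-therapeutic efficacy is expected there, but it is a forecast. It would also be wrong to infer that medians generally improve: among the four 10-patient examples the median moved only when every clearance came after the rescues. This is a low-cost improvement to a descriptive secondary analysis and leaves the primary hepatic analysis untouched.

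**What to change.** For PCT and FCT, report the Aalen-Johansen cumulative incidence of clearance, with rescue before clearance as a competing event and ordinary censoring for drop-out without rescue. Give the number rescued before clearance in each arm. The SAP's last update was after database lock, so present this as a labelled supplementary analysis beside the prespecified Kaplan-Meier and do not replace it.

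Keeping rescued patients in the risk set as not cleared to Day 29 is a simpler alternative, but it gives the same answer only when there is no other censoring.

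One definition needs settling first. SAP 2.4.2 counts only Coartem as rescue, while Protocol 5.5.6 gives failing Coartem-arm patients rescue under local guidance. The two passages must be reconciled so that the competing event is defined in that arm.

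The cost is a paragraph of SAP text and a little programming. The downside is that the median may not be reached in arms with much rescue.

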### **2.7.2.4 Recrudescence**

Recrudescence is defined as appearance of asexual parasites after clearance of initial infection with a genotype identical to that of parasites present at baseline. Recrudescence must be confirmed by PCR analysis.

Incidence rates of recrudescence at Study Day 29 will be estimated by Kaplan-Meier method based on the subset of FAS patients who have clearance of initial infection before Day 15. Time to recrudescence will be calculated from the time of first study medication to the date of first event if a patient experiences the event and be censored at the time of last parasite

assessment if a patient does not experience the event. Patients who experienced a new infection will be censored at the first time of new infection.

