9.5.1.4 Recrudescence

Reinfection is defined as appearance of asexual parasites after clearance of initial infection with a genotype different from those parasites present at baseline.

Recrudescence is defined as appearance of asexual parasites after clearance of initial infection with a genotype identical to that of parasites present at baseline. Recrudescence must be confirmed by PCR analysis.

Incidence rates of recrudescence at Study Day 29 will be estimated by Kaplan-Meier method based on the subset of FAS patients who have clearance of initial infection by Study Day 7. Time to recrudescence will be calculated from the time of first study medication to the date of first event if a patient experience the event and be censored at the time of last parasite assessment if a patient does not experience the event.

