**Fever Clearance time (FCT)**, defined as time from the first dose until the first time the axillary body temperature decreased below and remained below 37.5°C axillary or 38.0°C oral/tympanic/rectal for at least a further 24 hours.

**Parasite clearance time (PCT)**, defined as time from the first dose until the first total and continued disappearance of asexual parasite forms which remained at least a further 48 hours.

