### **Handling of missing values/censoring/discontinuations**

Patients whose outcome status cannot be determined due to incomplete/missing data will be excluded from analysis. Especially, the denominator is the number of patients who experience treatment failure or have malaria blood film result at Day 29 for LCF and LPF. Patients with ETF will be excluded from the analysis of LCF and patients with ETF or LCF will be excluded from the analysis of LPF.

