### **2.7.2.5 Time to event analysis for reinfection**

Reinfection is defined as appearance of asexual parasites after clearance of initial infection with a genotype different from those parasites present at baseline. Reinfection must be confirmed by PCR analysis.

Incidence rates of reinfection at Day 29 will be estimated by the Kaplan-Meier method based on the subset of FAS patients who have clearance of initial infection before Day 15.

Time to event (reinfection) will be calculated from the time of first study medication to the date of first event if a patient experiences the event and will be censored at the time of last parasite assessment if a patient does not experience the event. Patients who experienced recrudescence will be censored at the first time of recrudescence.

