### **Handling of missing values/censoring/discontinuations**

The patient will be censored at the time of last parasite assessment if a patient does not experience the event. Undertermined treatment failures due to missing PCR data will be considered as censored at the time of treatment failure.

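### The recrudescence and reinfection Kaplan-Meier analyses have no rule for rescue or other antimalarials, so as written they can count Coartem-treated time as KAE609 follow-up

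*SAP*

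**What the plan says.** SAP 2.7.2.4 estimates recrudescence at Day 29 by the "Kaplan-Meier method based on the subset of FAS patients who have clearance of initial infection before Day 15". Time runs from first study medication. A new infection censors; otherwise the patient is followed to the last parasite assessment. SAP 2.7.2.5 treats reinfection in the same way: "Patients who experienced recrudescence will be censored at the first time of recrudescence". Its handling paragraph repeats the default ("The patient will be censored at the time of last parasite assessment if a patient does not experience the event") and adds censoring at failure where PCR data are missing.

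Protocol 9.5.1.4 has the same structure, with an earlier clearance limit: "based on the subset of FAS patients who have clearance of initial infection by Study Day 7". None of these sections says what happens when a patient receives rescue medication or another antimalarial.

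Other analyses in the SAP do have a rule:

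- **PCT and FCT (2.7.2.3):** if rescue comes before clearance, "the time to event will be censored at the first use of rescue medication". The endpoint in Table 1-2 is worded to match: "Parasite and Fever Clearance Times (PCT and FCT) before rescue medication is given".
- **ACPR by Kaplan-Meier (2.7.2.1.1 and 2.7.2.1.2):** patients who took non-rescue antimalarials and are not non-responders are censored at the first such drug. In 2.7.2.1.1 the wording is limited to drugs for other infections.
- **Late failure proportions (2.7.2.2):** "Patients with ETF will be excluded from the analysis of LCF", and patients with ETF or LCF are left out of the LPF analysis.

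**The concern.** Rescued patients do not leave the study. Protocol 5.5.6 and 5.6.1 keep them on the full assessment schedule to Day 29, and the FAS analyses them in their randomised arm. A KAE609 patient who fails early, takes Coartem and clears before Day 15 therefore meets the literal entry condition. That patient then adds follow-up to the KAE609 denominator while treated with the comparator drug.

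Day 29 recrudescence is the only endpoint listed for the secondary objective on recrudescence (SAP Table 1-2). If rescued patients are counted, the rate mixes risk after KAE609 alone with risk after KAE609 plus Coartem, in proportions that depend on how many patients fail early in each arm. Two programmers working from the same text could also report different rates.

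**Working it through.** **1. Which patients are affected.** The plan gives no figure for this analysis, so there is nothing to reproduce. Tracing patients through the rules gives the following:

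| Course on KAE609 | Treatment under 2.7.2.4 as written |
|---|---|
| Clears, then PCR-confirmed recrudescence | Event |
| Clears, then PCR-confirmed new infection | Censored at new infection |
| Clears, then parasitaemia with PCR missing | Censored at failure |
| Rescued first (early failure, uncleared late failure, or second vomited dose), clears before Day 15 | At risk to last assessment |
| Clears, then an antimalarial without a recurrence | At risk to last assessment |

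Only the last two rows are at issue. Coartem given on Day 29 to unrescued KAE609 patients has no material effect, because SAP 2.1.1 truncates time at Day 29.

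**2. Inputs.** Arm sizes of 10 (Cohorts 1 and 2) and 20 (later cohorts) come from Protocol 3.1. All other counts are assumptions: recrudescences among unrescued patients at Days 15, 22, 22 (arm of 10) or Days 15, 22, 22, 29 (arm of 20), and everyone else followed to Day 29.

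**3. Formula.** Incidence = 1 − ∏(1 − d/n) over event days. If no one is censored between the first and last event, this reduces to events divided by patients at risk. With N patients, k rescued before clearing, r events among the unrescued and q among the rescued:

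- as written: (r + q)/N
- clearance required before rescue: r/(N − k)

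**4. Rescue before clearance, q = 0.**

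| N | k | r | As written | Clearance before rescue |
|---|---|---|---|---|
| 10 | 4 | 3 | 3/10 = 30.0% | 3/6 = 50.0% |
| 20 | 2 | 4 | 4/20 = 20.0% | 4/18 = 22.2% |
| 20 | 4 | 4 | 4/20 = 20.0% | 4/16 = 25.0% |
| any | 0 | any | equal | equal |

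Product-limit check for the first row: 1 − (9/10)(7/9) = 30.0%; 1 − (5/6)(3/5) = 50.0%.

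**5. Direction.** The as-written rate is the higher one when q/k exceeds r/(N − k). In the first row, q = 2 gives 5/10 = 50% (no gap) and q = 3 gives 6/10 = 60%, against 50%.

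**6. Drug after clearance, no recurrence.** This is what remains if clearance already means clearance before rescue.

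| N, events | Treated | Uncensored | Censored at Day 8 | Censored at Day 25 |
|---|---|---|---|---|
| 10, 3 | 1 | 30.0% | 3/9 = 33.3% | 30.0% |
| 10, 3 | 2 | 30.0% | 3/8 = 37.5% | 30.0% |
| 20, 4 | 1 | 20.0% | 4/19 = 21.1% | 20.3% |
| 20, 4 | 2 | 20.0% | 4/18 = 22.2% | 20.7% |

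**7. Precision.** Exact 95% intervals for the simple proportions are 12–88% (3/6), 7–65% (3/10), 6–48% (4/18) and 6–44% (4/20).

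**The case against.** The strongest reply is that clearance has one operational meaning in the SAP, the PCT variable. Table 1-2 limits it to the period before rescue, and 2.7.2.3, directly before the recrudescence section, censors anyone rescued first. Such a patient has no clearance event in the PCT data and would not enter the recrudescence subset. This is a reasonable reading, and it makes every gap in step 4 zero. After clearance, late failure requires renewed parasitaemia, which is already an event or censored. That leaves unusual cases: rescue on clinical judgement or after vomiting, or an antimalarial recorded as a deviation.

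The reply does not close the point. SAP 2.7.2.4 does not refer to the PCT variable. The PCT definition itself, "first total and continued disappearance of asexual parasite forms which remained at least a further 48 hours", has no rescue condition. The 2.7.2.3 rule censors a time to clearance; it does not say who enters a different analysis.

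A second reply is that following everyone in the randomised arm fits the intent-to-treat principle stated for the FAS. That is a legitimate choice, but the SAP does not say that it has been made for these two analyses.

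A reader might go further in two ways that the documents do not support:

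- **Intent.** The move from clearance by Day 7 to clearance before Day 15 might suggest that rescue-driven clearance was meant to qualify. The SAP document history logs the change without a reason, and visit timing or late unaided clearance could also explain it.
- **Size.** Protocol 3.6 gives early failure shares of 42% (10 mg) and 25% (20 mg), and recrudescence in 4 patients (36%). Combining them is unsafe. Four patients at 36% imply about 11 in total, whereas Protocol 9.8 lists 25 patients in the 10 to 30 mg study and 11 in the 75 mg study. The 36% may therefore belong to a different dose from the early failures.

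**Conclusion.** The gap is real: the two sections state an entry rule and a censoring rule, neither deals with rescue or other antimalarials, and the result departs from the SAP's conventions for PCT/FCT and the ACPR Kaplan-Meier curves. As written, the recrudescence rate would usually be diluted in arms with early failures, but the direction reverses if rescued patients recrudesce more often than the others.

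The size in this trial is unknown. On assumed counts the gap runs from zero to 20 percentage points, and the upper end needs 4 of 10 patients rescued before clearing. If clearance is read from the PCT variable, the remaining gap is 0 to 7.5 points in the cases shown, and near zero when the drug comes late.

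The point is minor. The endpoint is secondary and descriptive, with no hypothesis and no comparison with Coartem (SAP 2.7 and 2.7.2). Treatment failures and rescue use are tabulated separately (SAP 2.4.2 and 2.7.2.2), and the intervals are wider than any gap shown. The issue affects how a rate is read, not a test.

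**What to change.** In SAP 2.7.2.4 and 2.7.2.5:

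1. Restrict the at-risk set to FAS patients whose initial infection clears before any rescue or other antimalarial.
2. Censor at the first such drug given for a reason other than the event under analysis. Apply this to the Coartem arms as well, where rescue follows local guidance.
3. Report beside each estimate the number per arm excluded or censored for this reason.

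If counting time after rescue is intended as a treatment-policy choice, both sections should say so and the tables should be labelled accordingly. The SAP already has an addendum dated after database lock, so a change made now should also be dated as post-lock.

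The cost is two sentences, one censoring variable from rescue data already captured (SAP 2.4.2), and one table row. The at-risk set becomes slightly smaller in arms with early failures, and censoring at rescue may be informative. The restricted rate describes patients who cleared without help, not what rescued patients would have experienced, which is why the counts belong next to it.
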